The primary efficacy parameter will be the change from baseline to Week 6 in the MADRS total score. The primary analysis will be performed using a mixed-effects model for repeated measures with treatment group, country, ADT failure category (one ADT failure, more than one ADT failure), visit, and treatment group-by-visit interaction as fixed effects, and the baseline value and baseline-by-visit interaction as covariates. An unstructured covariance matrix will be used to model the covariance of within-patient scores. The Hochberg procedure will be used to control the overall type I error rate at a 0.05 level (2-sided) for multiple comparisons of 2 active doses with placebo for the primary endpoint.

Safety analyses will be based on the safety population consisting of all randomized patients who received at least 1 dose of DB investigational product. All safety parameters will be summarized descriptively.

Sample Size Calculation: The study will screen approximately 1700 patients to randomize 750 patients in a 1:1:1 ratio to cariprazine 1.5 mg/day + ADT, cariprazine 3 mg/day + ADT, and placebo + ADT groups. A sample size of 250 patients per arm will provide approximately 90% statistical power to show at least 1 of the 2 cariprazine doses is statistically significantly more efficacious than placebo in the primary endpoint, assuming an effect size of 0.286 and a dropout rate of 15% at Week 6. The sample size and power were calculated adjusting for multiple comparisons using the Hochberg procedure.

[figure not shown]
Figure 1 Study Schema

Table 1 Schedule of Visits and Procedures

Study Period	Screening	Baseline	Double-blind Treatment				Safety Follow-up
Visit	1	2	3	4	5	6/ET	7
Study Week	Up to -2 ^k	0	1	2	4	6 ^{a,b}	10
Study Day	Up to -14 ^k	1	8	15	29	43	71
Visit Windows		(within 14 days of start of screening procedures) ^k	± 3 Days	± 3 Days	± 3 Days	± 3 Days	± 3 Days
Informed Consent	X						
Verified Clinical Trials Check ^c	X						
Medical and Psychiatric Histories	X						
Prior Medication History	X						
Inclusion/Exclusion Criteria	X	X					
Randomization		X					
Clinical Laboratory Tests ^{d,e}	X					X	
Serum Pregnancy Test ^{d,e}	X					X	X
Hepatitis Serology	X						
Hemoglobin A1c	X						
Urine Drug Screen ^e	X						
Blood Alcohol Concentration (by Breathalyzer) ^e	X						
Vital Signs ^f	X	X	X	X	X	X	X
Electrocardiogram	X					X	
Physical Examination	X					X	
SCID-5	X						
SAFER Remote Telephone Interview ^g	X						

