6.6.3 Clinical Laboratory Determinations

Clinical laboratory tests will be performed according to the schedule in [Table 3](#). Patients will be asked to fast for at least 10 hours prior to any visit requiring clinical laboratory testing.

Table 3 Schedule of Clinical Laboratory Tests

Category	Visit Number(s)	Parameter(s)
Hepatitis Serology	1	Hepatitis C virus antibody, hepatitis B surface antigen, and hepatitis B core antibody total. Reflex hepatitis B core antibody immunoglobulin M will be performed for all hepatitis B core antibody total positive or reactive results. Reflex HCV RNA titer test will be performed for all Hepatitis C virus antibody positive or reactive results.
Screening Hemoglobin A1c	1	Hemoglobin A1c
Hematology	1 and Visit 6/ET	Absolute and differential white blood cell count, Absolute Neutrophil Count (ANC), erythrocyte count, hemoglobin, hematocrit, platelet count, and red blood cell indices (mean corpuscular volume, mean corpuscular hemoglobin, and mean corpuscular hemoglobin concentration)
Chemistry	1 and Visit 6/ET	Sodium, potassium, calcium, chloride, bicarbonate, glucose, blood urea nitrogen, creatinine, total protein, alkaline phosphatase, albumin, total bilirubin, direct bilirubin, indirect bilirubin, AST, ALT, free T3, free T4, TSH, lactate dehydrogenase, creatine phosphokinase, γ -glutamyl transpeptidase, uric acid, phosphate, lipid panel (total cholesterol, triglycerides, low-density lipoproteins, high-density lipoproteins), prolactin, insulin, and magnesium
Urine drug screen	1	Benzoylecgonine (cocaine), barbiturates, amphetamines, benzodiazepines, cannabinoids, opiates, methadone, phencyclidine
Urine myoglobin	1 and Visit 6/ET	Only in patients with creatine phosphokinase levels > 1000 U/L or as clinically indicated for any rise in creatine phosphokinase levels or as necessitated by symptoms
Urinalysis	1 and Visit 6/ET	Specific gravity, pH, protein, glucose, ketones, blood, nitrite, bilirubin, and microscopy (red blood cell count [high-power field], white blood cell count [high-power field], casts [low-power field], and crystals)
Blood alcohol concentration	1	Blood alcohol concentration by Breathalyzer
Serum β -hCG (women of childbearing potential only)	1, Visit 6/ET, and Visit 7 Safety Follow-up Visit	—
Repeat urine drug screen, blood alcohol level, and serum pregnancy test	At random upon request from the Investigator	—

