The number and percentage of participants with treatment-emergent significant changes in lipid parameters (total cholesterol, low-density lipoprotein cholesterol, high-density lipoprotein cholesterol, and triglycerides) and glucose will be tabulated by treatment group for the DB treatment period. The criteria for treatment-emergent significant changes in lipids and glucose is provided in [Table 10-2](#). Percentages will be calculated relative to the number of participants with baseline values meeting the specified baseline criteria and with at least 1 postbaseline assessment. The change in lipids and glucose from baseline to the highest (lowest for high-density lipoprotein cholesterol) postbaseline measurement will be summarized. Supportive listings of participants with treatment-emergent changes in lipids and glucose values will be provided.

The number and percentage of participants meeting potential Hy's Law criteria (elevation of alanine aminotransferase [ALT] or aspartate aminotransferase [AST] $\geq 3x$ ULN with total bilirubin [TBL] $\geq 2x$ ULN and alkaline phosphatase [ALP] $< 2x$ ULN in a 24-hour period) and Concurrent Elevations criteria in a 24-hour period will be tabulated by DB treatment group for the safety population. A supportive listing will be provided.

Concurrent Elevations in a 24-hour period are defined as:

1. ALT or AST $\geq 3x$ ULN and TBL $\geq 1.5 x$ ULN
2. ALT or AST $\geq 3x$ ULN and TBL $\geq 2 x$ ULN

Table 10-1 Clinical Laboratory PCS Criteria

Laboratory Parameter	SI Unit	PCS Criteria Low Values	PCS Criteria High Values
Hematology			
Hemoglobin	g/L	< 0.9 × LLN	—
Hematocrit	%	< 0.9 × LLN	—
Eosinophils	%	—	> 10
Neutrophils	%	< 30	> 90
Basophils	%	—	> 6
Monocytes	%	—	> 20
Lymphocytes	%	< 10	> 60
Absolute neutrophils	10 ⁹ /L	< 1.0	—
Platelet count	10 ⁹ /L	≤ 75	≥ 700
White cell count	10 ⁹ /L	≤ 2.5	≥ 15
Chemistry			
Albumin	g/L	< 0.9 × LLN	> 1.1 × ULN
Alkaline phosphatase	U/L	—	≥ 3 × ULN
ALT	U/L	—	≥ 3 × ULN
AST	U/L	—	≥ 3 × ULN
GGT	U/L	—	≥ 3 × ULN
LDH	U/L	—	≥ 3 × ULN
Blood urea nitrogen	mmol/L	—	> 1.2 × ULN
Calcium	mmol/L	< 0.9 × LLN	> 1.1 × ULN
Chloride	mmol/L	< 0.9 × LLN	> 1.1 × ULN
Cholesterol	mmol/L	—	> 1.3 × ULN
HDL	mmol/L	< 0.8 × LLN	—
LDL	mmol/L	—	> 1.2 × ULN
CPK	U/L	—	> 1.5 × ULN
Creatinine	μmol/L	—	> 1.3 × ULN
Glucose, fasting	mmol/L	< 0.8 × LLN	> 1.2 × ULN
Magnesium	mmol/L	< 0.9 × LLN	> 1.1 × ULN
Potassium	mmol/L	< 0.9 × LLN	> 1.1 × ULN
Sodium	mmol/L	< 0.9 × LLN	> 1.1 × ULN

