Total bilirubin	μmol/L	—	> 1.5 × ULN
Total protein	g/L	< 0.9 × LLN	> 1.1 × ULN
Triglycerides, fasting	mmol/L	—	> 1.2 × ULN
Uric acid	μmol /L	—	> 1.1 × ULN
Urinalysis			
Protein	—	—	At least 2 +
Glucose	—	—	At least 2 +
Blood	—	—	At least 2 +

ALT = alanine aminotransferase; AST = aspartate aminotransferase; CPK = creatine phosphokinase; GGT = gamma glutamyl transferase; HDL = high-density lipoprotein; LDH = lactate dehydrogenase; LDL = low-density lipoprotein; LLN = lower limit of normal laboratory reference range; PCS = potentially clinically significant; SI = *Le Système International d'Unités* (International System of Units); ULN = upper limit of normal laboratory reference range.

Laboratory Parameter	SI Unit	PCS Criteria Low Values	PCS Criteria High Values
-----------------------------	----------------	------------------------------------	-------------------------------------

Fasting: Includes both, fasting and unspecified fasting status.

Table 10-2 The Criteria for Treatment-emergent Significant Changes in Lipids and Glucose

Laboratory Parameter	Measurement	Category	Criteria
Total cholesterol (Fasting or Non-fasting)	Actual	Normal	< 200 mg/dL
		Borderline	≥ 200 and < 240 mg/dL
		Normal/Borderline	< 240 mg/dL
		High	≥ 240 mg/dL
		Borderline/High	≥ 200 mg/dL
	Change from baseline	Increase ≥ 40 mg/dL	Increase ≥ 40 mg/dL
LDL Cholesterol* (Fasting)	Actual	Normal	< 100 mg/dL
		Borderline	≥ 100 and < 160 mg/dL
		Normal/Borderline	< 160 mg/dL
		High	≥ 160 mg/dL
		Borderline/High	≥ 100 mg/dL
	Change from baseline	Increase ≥ 30 mg/dL	Increase ≥ 30 mg/dL
HDL Cholesterol (Fasting and Non-Fasting)	Actual	Normal	≥ 40 mg/dL
		Low	< 40 mg/dL
	Change from baseline	Decrease ≥ 20 mg/dL	Decrease ≥ 20 mg/dL
Triglycerides (Fasting)	Actual	Normal	< 150 mg/dL
		Borderline	≥ 150 and < 200 mg/dL
		Normal/ Borderline	< 200 mg/dL
		High	≥ 200 mg/dL
		Very High	≥ 500 mg/dL
		Borderline/High/Very High	≥ 150 mg/dL
		≥ 1000 mg/dL	≥ 1000 mg/dL
	Change from baseline	Increase ≥ 50 mg/dL	Increase ≥ 50 mg/dL
Triglycerides (Non-Fasting)	Actual	Very High	≥ 500 mg/dL
		≥ 1000 mg/dL	≥ 1000 mg/dL
	Change from baseline	Increase ≥ 10 mg/dL	Increase ≥ 10 mg/dL
Serum Glucose (Fasting)	Actual	Normal	< 100 mg/dL
		Impaired	≥ 100 and < 126 mg/dL
		Normal/ Impaired	< 126 mg/dL
		High	≥ 126 mg/dL
	Change from baseline	Increase ≥ 10 mg/dL	Increase ≥ 10 mg/dL
Serum Glucose (Non-Fasting)	Actual	Normal	< 140 mg/dL
		Borderline	≥ 140 and < 200 mg/dL

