		Normal/Borderline	< 200 mg/dL
		High	≥ 200 mg/dL
		Borderline/High	≥ 140 mg/dL
	Change from baseline	Increase ≥ 20 mg/dL	Increase ≥ 20 mg/dL

* LDL direct and LDL calculated are combined.

Fasting: Includes both, fasting and unspecified fasting status.

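### SAP Table 10-2 sets the non-fasting triglyceride change criterion (10 mg/dL) below the fasting one (50 mg/dL), the reverse of the glucose rows, and gives no reason

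*SAP*

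**What the plan says.** Table 10-2 in SAP Section 10.2 defines treatment-emergent significant changes in lipids and glucose. Two analytes have separate change-from-baseline rows for fasting and non-fasting samples:

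| Analyte | Fasting | Non-fasting |
|---|---|---|
| Triglycerides | "Increase ≥ 50 mg/dL" | "Increase ≥ 10 mg/dL" |
| Serum glucose | "Increase ≥ 10 mg/dL" | "Increase ≥ 20 mg/dL" |

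The non-fasting triglyceride entry and the fasting glucose entry have the same wording, and they stand in adjacent blocks. The non-fasting triglyceride figure is the same in the Category and Criteria columns, so it does not look like a table broken in extraction. The only other non-fasting triglyceride categories are actual values of at least 500 and at least 1000 mg/dL. No rationale is given for the 10 mg/dL figure.

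Three further provisions decide who reaches this row:

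- The table footnote reads "Fasting: Includes both, fasting and unspecified fasting status". Only samples positively recorded as non-fasting are assessed there.
- Protocol Section 6.6.3 states: "Patients will be asked to fast for at least 10 hours prior to any visit requiring clinical laboratory testing".
- Chemistry is scheduled at visits "1 and Visit 6/ET" (Protocol Table 3), which gives one planned postbaseline value.

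The counts for lipids and "glucose will be tabulated by treatment group for the DB treatment period", with supportive listings of the participants concerned. The Protocol Summary says of safety analyses: "All safety parameters will be summarized descriptively".

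**The concern.** Within one table, the two analytes that depend on fasting status are ordered in opposite ways. For glucose, the non-fasting criterion asks for a larger rise than the fasting one. For triglycerides it asks for a rise one fifth as large. The SAP offers nothing to explain why the direction should differ, and the odd value repeats the figure in the next block.

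Applied as written, the rule would label a 10 mg/dL rise as treatment-emergent and significant in a participant recorded as non-fasting. A rise of 40 mg/dL in a fasting participant would not be labelled. At stake is how one row of a metabolic safety table, and the listing attached to it, can be read. If the cut-off lies inside ordinary visit-to-visit variation, the row will contain many participants whose triglycerides have not truly moved.

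**Working it through.** The plan has no figure of its own to reproduce here, so the check has four parts.

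**1. Ratio of cut-offs.** 50 / 10 = 5. This compares thresholds, not flag rates.

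**2. Each change criterion as a share of the lowest actual-value cut-off in its own block of Table 10-2.**

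| Row | Calculation | Share |
|---|---|---|
| Total cholesterol | 40 / 200 | 20% |
| LDL | 30 / 100 | 30% |
| HDL | 20 / 40 | 50% |
| Triglycerides, fasting | 50 / 150 | 33% |
| Glucose, fasting | 10 / 100 | 10% |
| Glucose, non-fasting | 20 / 140 | 14% |
| Triglycerides, non-fasting | 10 / 500 | 2% |

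The 2% is somewhat unfair, because the non-fasting triglyceride block starts at its very high category. Measured against the fasting triglyceride cut-off instead, the share is 10 / 150 = 6.7%, which is still the lowest.

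**3. Chance flags when nothing has changed.** The documents give no SD for triglycerides, so a within-person SD *s* of 30 to 60 mg/dL per measurement is assumed. I also assume normal, independent errors and one postbaseline value. The SD of a change is then √2 × *s*, and the probability of a flag at threshold *t* is 1 − Φ(*t* / (√2 *s*)).

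| *s* | SD of change | *t* = 10 | *t* = 50 | Ratio of rates |
|---|---|---|---|---|
| 30 | 42.4 | 1 − Φ(0.236) = 0.407 | 1 − Φ(1.179) = 0.119 | 3.4 |
| 60 | 84.9 | 1 − Φ(0.118) = 0.453 | 1 − Φ(0.589) = 0.278 | 1.6 |

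With symmetric error, half of unchanged participants show a rise of some size. A flag rate of 41 to 45% is therefore close to counting any rise at all. Varying the SD of change itself from 20 to 80 mg/dL gives 31 to 45% at the 10 mg/dL threshold and 0.6 to 27% at 50 mg/dL. The ratio of rates then runs from about 50 down to 1.7.

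**4. What this does to a comparison between arms.** Chance flags arise in every arm, placebo included. Suppose a drug effect takes the form of large rises in some participants, who would be flagged under either threshold. Each such participant adds 1 minus the background rate to the expected count:

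- *s* = 30: 1 − 0.407 = 0.593 at 10 mg/dL, against 1 − 0.119 = 0.881 at 50 mg/dL.
- *s* = 60: 1 − 0.453 = 0.547 at 10 mg/dL, against 1 − 0.278 = 0.722 at 50 mg/dL.

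The contrast is diluted but does not disappear. For a small uniform shift, it is the ratio between arms that is pulled towards 1; the absolute difference need not shrink.

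**Scale.** The documents give no non-fasting fraction. If 5% of the planned 250 per arm were recorded as non-fasting (an assumption), that is 12.5 participants. Expected chance flags are 12.5 × 0.407 to 12.5 × 0.453, or about 5 to 6 per arm. At the 50 mg/dL threshold they would be 12.5 × 0.119 to 12.5 × 0.278, or about 1.5 to 3.5.

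**The case against.** The strongest reply is that this is one row among seven change rows, fed by few participants, in a descriptive table. That is right, and it limits the point. Triglyceride effects would still show in the fasting change row and the fasting categories, in the non-fasting 500 and 1000 mg/dL categories, and in the potentially clinically significant criterion of Table 10-1. They would also show in the descriptive changes in SI and conventional units, and in the summary of change to the highest postbaseline value. No hypothesis test uses this row.

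A second reply is that nothing in the SAP requires a non-fasting criterion to be at least as large as the fasting one, so the sponsor may have had a reason. That also stands in part. The glucose ordering and the repeated value suggest an error without establishing it, which is why the remedy begins with a check of the sponsor's standard. But the SAP states no reason, and I can construct none from the documents that makes the two triglyceride rows coherent.

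Three stronger readings are tempting and are not supported:

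- A reader might infer that the non-fasting flag is five times as sensitive. Five is the ratio of cut-offs; the ratio of flag rates depends on the SD and has no fixed value.
- A reader might infer that the table as a whole would mostly count noise, or that a large share of every arm would be flagged. The 41 to 45% applies only to participants with samples recorded as non-fasting.
- A reader might infer that the row hides any real difference between arms. Dilution within one row does not conceal what the other outputs show.

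**Conclusion.** The inconsistency is real and minor. The two triglyceride change criteria run opposite to the two glucose criteria in the same table, without explanation, and the lower value matches the neighbouring fasting glucose entry. As written, the non-fasting triglyceride change row is weakly specific and would flag roughly two in five unchanged participants who reach it.

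That size rests on an assumed within-person SD of 30 to 60 mg/dL and normal errors. The number of participants affected rests on an unknown non-fasting fraction, probably small given the fasting request and the footnote. The ordering of the cut-offs needs no assumption, because it stands in the table. Primary and key secondary inference are not involved.

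**What to change.** Before unblinding, check the non-fasting triglyceride change cell against the fasting row and the sponsor's laboratory standard. Then either correct it so that it is not below the fasting criterion, or delete the non-fasting change row and keep only the 500 and 1000 mg/dL categories. I propose no replacement value, because the documents give no basis for one.

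The cost is one table cell (or one deleted row), a line in the SAP change summary, and the matching edit to the table and listing programs. No data collection changes.

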10.3 VITAL SIGNS

Descriptive statistics for vital signs (supine radial pulse rate, supine systolic and diastolic BP, body weight, waist circumference, BMI and temperature) and changes from baseline values at each visit and at the end of the double-blind treatment period will be presented by treatment group.

Vital sign values will be PCS if they meet both the observed-value criteria and the change from baseline value criteria. The criteria for PCS vital sign values are provided in Table 10-3. The percentages will be calculated relative to the number of participants with baseline values and at least 1 postbaseline assessment. The numerator will be the total number of participants with available baseline values and at least 1 PCS postbaseline value. A supportive listing of participants with postbaseline PCS values will be provided, including the participant identification number, study center number, and baseline and postbaseline values. A listing of all AEs occurring in participants who have PCS vital sign values will also be provided.

Table 10-3 Criteria for Potentially Clinically Significant Vital Signs

Parameter	Flag	Criteria	
		Observed Value	Change From Baseline
Supine systolic blood pressure, mm Hg ^a	High	≥ 180	Increase of ≥ 20
	Low	≤ 90	Decrease of ≥ 20
Supine diastolic blood pressure, mm Hg ^a	High	≥ 105	Increase of ≥ 15
	Low	≤ 50	Decrease of ≥ 15
Supine pulse rate, bpm ^a	High	≥ 120	Increase of ≥ 15
	Low	≤ 50	Decrease of ≥ 15
Weight, kg	High	—	Increase of ≥ 7%
	Low	—	Decrease of ≥ 7%

a A postbaseline value is considered potentially clinically significant if it meets both the observed-value and the change-from-baseline criteria.

bpm = beats per minute.

The number and percentage of participants with PCS weight increase or decrease will also be provided by baseline BMI categories (underweight [$< 18.5 \text{ kg/m}^2$], normal [≥ 18.5 and $< 25 \text{ kg/m}^2$], overweight [≥ 25 and $< 30 \text{ kg/m}^2$], and obese [$\geq 30 \text{ kg/m}^2$]) by treatment group for the safety population.

The number and percentage of participants with orthostatic hypotension will be provided by treatment group. Orthostatic hypotension is defined as a reduction of ≥ 20 mm Hg in systolic BP or a reduction of ≥ 10 mm Hg in diastolic BP measured after the participant stands up after resting in the supine position. Standing measurements should be taken after a sufficient amount of time has passed to allow the BP to equilibrate in the standing state. A supportive listing will be provided including the participant identification number, study center number, and baseline and postbaseline systolic and diastolic BP values (supine and standing). A listing of all AEs occurring in participants who have orthostatic hypertension will also be provided.

As specified in the Seventh Report of the Joint National Committee on prevention, detection, evaluation and treatment of high blood pressure ([NIH Publication No. 04-5230, 2004](#)), hypertension status is defined as:

- Normotensive: supine SBP < 120 mm Hg and DBP < 80 mm Hg.
- Prehypertension: supine SBP 120 to 139 mm Hg or DBP 80 to 89 mm Hg.
- Stage I Hypertension: supine SBP 140 to 159 mm Hg or DBP 90 to 99 mm Hg.
- Stage II Hypertension: supine SBP ≥ 160 mm Hg or DBP ≥ 100 mm Hg.

Tabulations showing the number and percentage of participants with hypertension status changes from baseline will be provided for:

- Shift of hypertension status from baseline to end of the DB treatment period
- Shift of hypertension status from baseline to highest category during the DB treatment period

Supportive listings of participants who have a shift in hypertension status from normotensive/prehypertension at Baseline to stage I/stage II hypertension will be provided.

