6.6.4 Vital Signs

Vital sign assessments will include radial pulse rate, systolic and diastolic BP, body weight, waist circumference and temperature. BP, pulse rate, temperature, and body weight will be measured at all visits. Whenever possible, the patient's weight should be measured at the same time of day. Patients should wear their usual indoor clothing but remove their jackets and shoes.

Height (without shoes) will be measured at Visit 1 (Screening) only.

Waist circumference will be measured at Visits 2 and 6/early termination (ET).

BP and radial pulse rate will be measured in the supine position followed by the standing position. The standing measurements must be measured after a sufficient amount of time has been given to allow the BP to equilibrate in the standing state. Radial pulse rate should be measured after BP measurements. BP and radial pulse may be measured manually or by machine.

All BP and radial pulse rate measurements will be recorded in the source documents and eCRF. Patients should be instructed not to wear clothing with tight sleeves when they come for clinic visits. Additionally, patients should be kept as calm and undisturbed as possible while BP and pulse rate measurements are taken (eg, there should be no talking while the BP is being measured). The same arm and BP cuff should be used for all BP measurements.

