7.3.3.3 Vital Signs

Descriptive statistics for vital signs and changes from baseline values at each visit and at the end of the DB treatment period will be presented by treatment group.

Vital sign values will be PCS if they meet both the observed-value criteria and the change from baseline value criteria. The criteria for PCS vital sign values will be detailed in the SAP. The percentages will be calculated relative to the number of patients with baseline values and at least 1 postbaseline assessment. The numerator will be the total number of patients with available baseline values and at least 1 PCS postbaseline value. A supportive listing of patients with postbaseline PCS values will be provided, including the patient identification number, study center number, and baseline and postbaseline values. A listing of all AEs occurring in patients who have PCS vital sign values will also be provided.

The number and percentage of patients with orthostatic hypotension will be provided by treatment group. Orthostatic hypotension is defined as a reduction of ≥ 20 mm Hg in systolic BP or a reduction of ≥ 10 mm Hg in diastolic BP measured after the patient stands up after resting in the supine position. Standing measurements should be taken after a sufficient amount of time has passed to allow the BP to equilibrate in the standing state. A supportive listing will be provided including the patient identification number, study center number, and baseline and postbaseline systolic and diastolic BP values (supine and standing).

The definition of different hypertension status will be detailed in the SAP.

Tabulations showing the number and percentage of patients with hypertension status changes from baseline will be provided for:

- Shift of hypertension status from baseline to end of the DB treatment period
- Shift of hypertension status from baseline to highest category during the DB treatment period

Supportive listings of patients who have a shift in hypertension status from normotensive/prehypertension at Baseline to stage I/stage II hypertension will be provided.

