12.2.4.5 Vital Signs

If visit is being performed remotely, this assessment may be omitted at the protocol-specified timepoint. Vital signs should be obtained at the next scheduled in-home or in-person visit.

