The safety analysis will be performed using the safety population for the double-blind treatment period and safety follow-up period. The double-blind treatment period starts with the first dose of double-blind investigational product and ends with the last scheduled assessment at Visit 6 (Week 6) or early termination (before Week 6). The safety follow-up period starts the day after the last scheduled assessment at Visit 6 (or early termination) and ends with the last safety follow-up visit. The safety parameters will include adverse events (AEs), clinical laboratory parameters, vital signs, electrocardiogram (ECG) parameters, EPS scales, the C-SSRS and the YMRS. For each safety parameter, the last assessment made before the first dose of double-blind investigational product will be used as the baseline for all analyses of that safety parameter. The summarization will be by treatment group for both double-blind and safety follow-up periods. Continuous variables will be summarized by number of participants and mean, SD, median, minimum, and maximum values. Categorical variables will be summarized by number and percentage of participants.

10.1 **ADVERSE EVENTS**

Adverse events will be coded by system organ class and preferred term using the *Medical Dictionary for Regulatory Activities*, version 24.0.

An adverse event (AE) will be considered a treatment-emergent adverse event (TEAE) if the AE began or worsened (increased in severity or became serious) on or after the first dose of DB investigational product. Per case report form instructions, a new AE record will be created with a new AE onset date for any AE that worsens. Therefore, TEAEs can simply be identified as those AEs with recorded onset date (and time, if known) on or after the date of the first dose of study intervention.

An AE will be considered a TESAE if it is a TEAE that additionally meets any SAE criterion.

For the DB treatment period, the number and percentage of participants reporting TEAEs in each treatment group will be tabulated by system organ class and preferred term; by system organ class, preferred term, and severity; and by system organ class, preferred term, and relationship to the IP. If more than 1 AE is coded to the same preferred term for the same participant, the participant will be counted only once for that preferred term using the most severe and most related occurrence for the summarization by severity and by relationship to the IP.

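### The orthostatic hypotension table has no baseline-negative condition, so its percentage mixes recurrent baseline cases with new ones; a treatment-emergent line would separate them

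*SAP*

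**What the plan says.** SAP 10.3 states: "The number and percentage of participants with orthostatic hypotension will be provided by treatment group". Protocol 7.3.3.3 carries the same sentence: "The number and percentage of patients with orthostatic hypotension will be provided by treatment group". Both define a case as a drop on standing of at least 20 mm Hg systolic or 10 mm Hg diastolic. Neither refers to the participant's status before dosing. A supporting listing is to show supine and standing pressures at baseline and after it.

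SAP 10.0 supplies the general frame: "The safety analysis will be performed using the safety population for the double-blind treatment period and safety follow-up period". It starts the double-blind period at the first dose and defines baseline as the last assessment before that dose.

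The data for a baseline condition are collected. Protocol 6.6.4 says "BP and radial pulse rate will be measured in the supine position followed by the standing position", and blood pressure is taken at all visits.

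**The concern.** A safety table of this kind is usually read to learn whether the drug causes new events. Here the numerator holds two groups: participants who become orthostatic on treatment, and participants who already were and are again. The table cannot tell them apart.

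The line also carries some weight. The descriptive statistics, the potentially clinically significant (PCS) criteria and the hypertension categories in SAP 10.3 all use supine pressure. The orthostatic line is therefore the only by-arm summary of standing blood pressure that the section specifies. What is at stake is how clearly a descriptive table shows onset; no confirmatory result is affected.

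**Working it through.** **How the SAP treats baseline in its other binary safety summaries**

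- Laboratory PCS (10.2) and ECG PCS (10.4): numerator and denominator are limited to participants who were non-PCS at baseline.
- SAS parkinsonism and BARS akathisia (10.5.2): the score must be at or below the threshold at baseline.
- Hypertension status (10.3): shown as a shift from baseline.
- PCS vital signs (10.3): a change from baseline is required, but everyone with a baseline value stays in the denominator: "The percentages will be calculated relative to the number of participants with baseline values and at least 1 postbaseline assessment". This rule serves Table 10-3, which has no orthostatic row.
- YMRS mania (10.5.1) and C-SSRS counts (10.5.3): no baseline condition.

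So there is no uniform rule, but most of the comparable summaries account for baseline and the orthostatic line does not.

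**Size under assumed rates**

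The documents state no figure for orthostatic hypotension, so there is nothing to reproduce. Let b be baseline prevalence, k the share of baseline cases positive again after dosing, and n0 and n1 the onset risks on placebo and drug among baseline-negative participants. All four are assumptions. The 250 per arm comes from SAP 13.0.

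- Planned rate: p = b·k + (1 − b)·n. Treatment-emergent rate: n.
- With equal k, planned difference = (1 − b)(n1 − n0).
- Planned ratio = w·(k1/k0) + (1 − w)·(n1/n0), where w = b·k0/p0 is the share of placebo cases that were baseline-positive. With k1 = k0 the first term is w × 1, which pulls the ratio toward 1.

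Scenario A: onset 3% vs 8%, treatment-emergent ratio 2.67, difference 5.0 points.

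| b | ratio, k = 0.3 | ratio, k = 0.5 | ratio, k = 1.0 | difference (points) |
|---|---|---|---|---|
| 2% | 2.38 | 2.24 | 1.99 | 4.90 |
| 5% | 2.09 | 1.89 | 1.61 | 4.75 |
| 10% | 1.79 | 1.58 | 1.35 | 4.50 |
| 15% | 1.60 | 1.42 | 1.24 | 4.25 |

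Example, b = 10% and k = 0.5: placebo 0.05 + 0.9 × 0.03 = 7.7%; drug 0.05 + 0.9 × 0.08 = 12.2%; ratio 1.58.

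Scenario B: onset 10% vs 15%, treatment-emergent ratio 1.50. At k = 0.5 the planned ratio is 1.45, 1.40, 1.32 and 1.27 for b = 2%, 5%, 10% and 15%. The differences are as in Scenario A.

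Share of placebo cases that were baseline-positive, at k = 0.5:

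- Scenario A: 0.010/0.0394 = 25% at b = 2%; 0.075/0.1005 = 75% at b = 15%.
- Scenario B: 0.010/0.108 = 9% at b = 2%; 0.075/0.160 = 47% at b = 15%.

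The k = 1.0 column is an outer bound in which every baseline case recurs.

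**Absolute scale.** With equal k, the loss in the difference is 0.10 to 0.75 points, or 0.25 to 1.9 participants per 250.

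**Unequal persistence.** The difference becomes (1 − b) × 5.0 + b × (k1 − k0) × 100 points, so it shrinks only if the drug raises persistence by less than 5 points. At k = 0.5 vs 0.6 in Scenario A it is 5.1 points at b = 2% (3.94% vs 9.04%, ratio 2.29) and 5.5 points at b = 10% (7.7% vs 13.2%, ratio 1.71).

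**The case against.** The strongest reply is that observed on-treatment frequency by randomized arm is a legitimate safety summary, that the line is nowhere called treatment-emergent, and that no rule in the plan is broken. That stands: this is a less informative analysis, not a mislabelled or biased one.

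New cases are also partly visible elsewhere. The listing lets a reader sort cases by hand. Orthostatic hypotension reported as an adverse event falls under SAP 10.1: "An adverse event (AE) will be considered a treatment-emergent adverse event (TEAE) if the AE began or worsened". Neither route, however, gives a rate of new blood-pressure-defined cases by arm.

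SAP 3.0 places table specifications in a separate document, which may already set a baseline condition. This cannot be ruled out.

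A reader might infer three stronger points that the documents do not support:

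- **That there is no denominator.** SAP 10.0 makes the safety population the default. What is missing is detail: whether a participant needs a postbaseline supine and standing pair. For remote visits Protocol 12.2.4.5 says "If visit is being performed remotely, this assessment may be omitted at the protocol-specified timepoint", but it asks for vital signs at the next in-home or in-person visit. Only participants with no postbaseline pair at all would matter.
- **That the plan does not say which readings count.** SAP 10.0 confines the summary to the double-blind and follow-up periods.
- **That baseline readings could enter the numerator.** Baseline precedes the first dose, and so lies outside both periods.

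**Conclusion.** The point holds as a cheap improvement to a descriptive safety table. As written, the percentage is on-treatment prevalence and cannot show new onset. Randomization keeps the arm comparison valid, and the primary and key secondary analyses are untouched.

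The pull of the risk ratio toward 1 rests on similar persistence across arms. Its size depends on prevalence, persistence and onset rates that the documents do not give; the figures above are illustrations only. The effect is small if baseline prevalence is low, which is plausible at ages 18 to 65 with clinically significant or unstable cardiovascular disease excluded. The risk difference changes little under equal persistence and can grow if the drug raises persistence.

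**What to change.** Add a treatment-emergent line to SAP 10.3:

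- **Numerator:** participants who do not meet the orthostatic criteria at the last predose assessment and meet them at one or more double-blind assessments.
- **Denominator:** participants negative at baseline with at least one double-blind supine and standing pair.

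Keep the overall postbaseline count as a second line with its denominator stated, so that recurrence in baseline-positive participants remains visible. If the table specifications already do this, copy the rule into the SAP.

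The cost is one sentence and one table line, with no new data. The new line's denominator is slightly smaller: 250 × (1 − b), or 245 at b = 2% and 225 at b = 10%, before removing anyone without a pair. Its limit is that baseline status rests on a single reading. A participant with intermittent orthostatic falls who is negative on that reading would be counted as new if positive at any of up to four double-blind visits.
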